5.4 Preparation and Administration of Study Drug

Study drug will be maintained and dispensed by the Investigational Drug Service (IDS) of the University of Pennsylvania ([name], contact person: [name] Jr., [contact] / [contact]). Commercially sourced celecoxib and naproxen will be blinded by IDS to match the placebo by over-encapsulation. As noted in section 5.7 (Packaging), the IDS will prepare blister packs of blinded study drug. The study drugs will be administered orally.

5.5 Subject Compliance Monitoring

Subjects will be instructed to take the study medications twice a day (at approximately 8 AM and 8 PM) on an empty stomach with a full glass of water. During each treatment phase, subjects will receive a reminder to take each study medication dose by email and/or text message twice a day. Reminder emails will be sent through Redcap, an on-line research electronic data capturing software, and will include a unique link to a survey to confirm taking the dose. Text message reminders will be sent through the HIPAA-compliant Clienttell system in use at the University of Pennsylvania Health System. The daily administration of drugs will be monitored by requesting the patient to confirm taking each pill at the time of dosing through Redcap or by the subject replying to the text message. Those forgetting to take the pill will be reminded by phone. Meanwhile, pill count and plasma drug concentration will also be used to verify adherence.

5.6 Prior and Concomitant Therapy

A full medication history will be taken at the screening visit. Subjects will be permitted to take oral contraceptives, hormone replacement therapy, thyroid replacement hormones, anti-hyperlipidemic agents, or anti-hypertensive agents during the study. Individuals taking other/additional chronic stable medications can be considered on a case-by-case basis for inclusion in the study if agreed upon by judgment of the investigators.

Subjects will not be permitted to take NSAIDs, antisecretory agents, or dietary or herbal supplements for 2 weeks prior to study drug administration and throughout the study. Any subject who has ever taken an anti-platelet or anti-coagulant medication will not be enrolled in the study (see Exclusion Criteria).

5.7 Packaging

Study drug will be supplied in bulk shipments and blinded by over-encapsulation by the IDS. The IDS will package blinded study medication on-site, as blister packs containing twelve capsules per blister pack. Each blister pack represents the drug supply for at-home drug treatment for a single treatment phase. The last dose, which will be administered on Day 7 in the CTRC, will be packaged separately. Subject

study drug supply will be packaged in kits of 3 blister packs plus the last study medication dose, one for each treatment phase. Each kit will represent the entire drug supply for one study subject.

5.8 Blinding of Study Drug

Blinding of the study drugs will be done by over-encapsulation at the Investigational Drug Service. All subjects and research staff will be blinded as to the sequence of study medications until the subject has completed the study. Codes linking randomization number for each subject to actual treatment will be secured in a sealed, opaque envelope and maintained in a locked drawer in the IDS. Research subjects will be given the emergency contact number for the study during the consenting process (see Attachment 2)

See section 8.4 (Unblinding Procedures) for a description of the process for unblinding a study subject.

5.9 Receiving, Storage, Dispensing and Return

5.9.1 Receipt of Drug Supplies

Upon receipt of the of the study treatment supplies, an inventory will be performed and a drug receipt log filled out and signed by the person accepting the shipment. The IDS designated staff will count and verify that the shipment contains all the items noted in the shipment inventory. Any damaged or unusable study drug in a given shipment will be documented in the study files. The investigator will notify the supplier of any damaged or unusable study treatments that were supplied to the investigator's site.

5.9.2 Storage

Stock study drug and drug packaged in patient kits within the IDS, and study drug that has been dispensed to the Investigator, will be stored in a locked cabinets with climate control maintaining the temperatures within a range of 20°-25° C (68°-77° F). Access to study drug within the IDS will be controlled by the IDS staff, and access to study drug dispensed to the Investigator will be controlled by the Investigator and the Investigator's study staff.

5.9.3 Dispensing of Study Drug

All study drugs will be dispensed as subject-specific kits by the IDS to the investigator or their designated study staff. The investigator or designated study staff will then dispense the appropriate amount of study drug from the study kit to the research subject assigned to that kit. For safety, the first dose will be administered while at the CTRC including a post-dose observational period to screen for acute adverse effects.

5.9.4 Return or Destruction of Study Drug

At the completion of the study, there will be a final reconciliation of drug shipped, drug consumed, and drug remaining. This reconciliation will be logged on the drug reconciliation form, signed and dated. Any discrepancies noted will be investigated, resolved, and documented prior to return or destruction of unused study drug. Drug destroyed on site will be documented in the study files.

6 Study Procedures

See Attachment 1 for the Study Procedure Flowchart.

6.1 Laboratory screens for compliance

6.1.1 Cotinine

Urinary cotinine, the nicotine metabolite indicating recent tobacco or nicotine use, will be qualitatively assessed per One-Step Rapid Nicotine (COT) Test, Craig Medical Distribution, Inc., [name] (or similar). This immunoassay detects cotinine at a cut-off sensitivity level of 200 ng/ml.

6.1.2 Protocol Non-Conform Drugs

Urine will be used to assess intake of protocol non-conform drugs by means of the Rapid Detect 10 Panel Test Dip Card, Rapid Detect, Inc., [name] (or similar). The drug screen includes for example Amphetamines (AMP), cocaine (COC), Tetrahydrocannabinol (THC), methamphetamine (mAMP), opiates (OPI), Phencyclidine (PCP), benzodiazepines (BZO), tricyclic antidepressants (TCA), barbiturates (BAR), and methadone (MTD).

6.1.3 Pregnancy test

Serum beta-HCG concentrations and a standard pregnancy urine dip test will be used to rule out pregnancy.

6.1.4 NSAID plasma concentrations

Prior to beginning each treatment phase, the concentrations of the four most commonly used NSAIDs in subjects' plasma will be quantified by LC-MS/MS. This will be done to confirm that subjects have not used any NSAIDs prior to beginning the treatment phase. During each treatment phase, study drug plasma concentrations will be quantified by LC-MS/MS to verify compliance and evaluate the pharmacokinetic profile of the study drugs. These assays are routinely performed in the Center for Experimental Therapeutics mass spectrometry laboratories.

6.1.5 COX-1 acetylation

COX-1 acetylation will be quantified to confirm that the subjects have not used any aspirin or aspirincontaining products.

Peripheral blood anticoagulated with citrate solution will be centrifuged immediately (180 g,10 min, 21°C) using a swing bucket centrifuge. Platelet rich plasma (PRP) will be removed, diluted with an equal volume PIPES buffer (pH 6.8), and 1 μM prostaglandin (PG) E₁ added and washed with PIPES buffer once. The platelets will be lyzed with RIPA buffer supplemented with protease inhibitor cocktail (Roche, Mannheim, Germany) at room temperature for 30 min. The soluble proteins in the supernatant will be collected by centrifugation at 4°C for 10 min. Proteins will be separated on NuPAGE® precast gels (Invitrogen) and stained with colloidal blue staining kit (Invitrogen). The molecular weight region corresponding to purified COX-1 (Cayman Chemical, Ann Arbor, MI) will be excised and cut into small pieces, which were then destained in 40% acetonitrile solution and dried. The gel pellet will be rehydrated in 20 μl of 12 ng/μl trypsin in 0.01% ProteaseMAXTM Surfactant (Promega, Madision, WI): 50mM NH4HCO3 for 10 min, which is covered with 30 μl of 0.01% ProteaseMAXTM Surfactant: 50mM NH4HCO3 and 10 μl heavy internal standards (250 fmol). Peptide standards IGAPFSLK, IGAPFS[+ace]LK and LVLTVR, and their heavy isotopic labeled peptides IGAPFSL[¹³C6;¹⁵N]K, IGA[¹³C3;¹⁵N]PFS[+ace]LK and LVLTV[¹³C5;¹⁵N]R were synthesized by Thermo Scientific (Bremen, Germany) for isotope dilution mass spectrometry. The protein digestion will be performed at 37°C for 2 hours.

Peptide liquid chromatography-mass spectrometry will be performed on an Eksigent NanoLC-2D system (Eksigent Technologies, Dublin, CA) coupled to a Thermo LTQ-FT mass spectrometer. Solvents used will be 0.5% ACN/0.1% formic acid (mobile phase A) and 98% ACN/0.1% formic acid (mobile phase B). Peptides will be loaded on an IntegraFrit™ trap column (10 mm×75 μm, New Objective, Woburn, MA), then the LC gradient run at 1 μL/min to separate peptides on a Magic C18 column (50 mm×0.2 mm, Michrom BioResources). A linear gradient of mobile phase B will be developed to elute peptides from 5% to 30% B at 1 min to 20 min. Nano electrospray ionization will be performed in the positive ion mode. The mass spectrometer was operated in MRM mode including 10 transitions in a single LC−MRM/MS analysis. The transitions for non-acetylated peptides, acetylated peptides and control peptides will be monitored. Typical instrument settings included a capillary temperature of 200 °C using nitrogen as an auxiliary gas. Helium is used as the collision gas. The activation energy (Act. Q) is 0.35 (arbitrary units). The MRM peak areas will be extracted and analyzed manually.

6.2 Questionnaires

6.2.1 Food questionnaires

6.2.1.1 3-day food record

The 3-day food record will be collected and analyzed by using Nutrition Data System for Research (NDSR).

6.2.1.2 24-hour dietary recall

The 24-hour dietary recalls will be collected using Nutrition Data System for Research (NDSR), a computer-based software application developed at the University of Minnesota Nutrition Coordinating Center (NCC) that facilitates the collection of recalls in a standardized fashion. To Dietary intake data gathered by interview is governed by a multiple-pass interview approach. Five distinct passes provide multiple opportunities for the participant to recall food intake. The first pass involves obtaining from the participant a listing of all foods and beverages consumed in the previous 24 hours. This listing is reviewed with the participant for completeness and correctness (second pass). The interviewer then collects detailed information about each reported food and beverage, including the amount consumed and method of preparation (third pass). In the optional fourth pass, the interviewer then probes for commonly forgotten foods. Finally, the detailed information is reviewed for completeness and correctness (fifth pass).

Dietary supplement use will be assessed in conjunction with collection of 24-hour dietary recalls using the Dietary Supplement Assessment Module included in NDSR.¹⁹ Use of all types of dietary supplements and non-prescription antacids are queried in the module.

The NCC Food and Nutrient Database serves as the source of food composition information in NDSR. ²⁰ This database includes over 18,000 foods including 7,000 brand name products. Ingredient choices and preparation methods provide more than 160,000 food variants. Values for 163 nutrient, nutrient ratios and other food components are generated from the database. The USDA Nutrient Data Laboratory is the primary source of nutrient values and nutrient composition. These values are supplemented by food manufacturers' information and data available in the scientific literature.²¹ Standardized, published imputation procedures are applied to minimize missing values.²²

6.2.2 International Physical Activity Questionnaire

The physical activity will be assessed using the "International Physical Activity Questionnaire" (October 2002) in the "long last 7 days self-administered format" for "use with young and middle-aged adults (15-69 years)" (Source: www.ipaq.ki.se). This questionnaire comprises five activity domains asked independently and has been frequently validated internationally to obtain comparable data on health-related physical activity. The scoring protocol for the IPAQ long form (updated Nov 2005) is available at www.ipaq.ki.se/IPAQ.asp?mnu sel=EEF&pg sel=IIA. The questionnaire is provided in the Attachments.

6.3 Measurements of COX activity

The activity of COX-1 and -2 will be assessed by the use of two *ex vivo* assays: inhibition of platelet TxA_2 formation, which is reflective of COX-1 activity;²³ and inhibition of PGE₂ formation by monocytes in which COX-2 is induced by endotoxin (LPS) and constitutive COX-1 is blocked by aspirin.²⁴ The urinary prostaglandin metabolite, 2,3 dinor-6 keto PGF_{1 α} (PGI-M) is measured by GC/MS, the thromboxane metabolite, 11-dehydro thromboxane B₂ (Tx-M) and 7 α -hydroxy-5, 11-diketotetranorprostane-1, 16-dioic acid (PGE-M), are quantified as its methoxyamine derivative by LC/MS/MS. These assays are routinely performed in the Center for Experimental Therapeutics mass spectrometry laboratories with inter- and intra-assay variability of 4-8%.

6.4 Genetic Analyses

Genetic analysis will be performed using High Throughput Sequencing (HTS) technology. These analyses will be performed at the High Throughput Sequencing Facility of the Penn Genomics Frontiers Institute (PGFI) using the Illumina HiSeq 2000 platform. Both whole exome and whole genome sequencing will be performed. This will allow high quality variant calling of approximately 3 million SNPs and insertions and deletions (Indels). It will also allow identifying Copy Number Variations (CNV) and other structural rearrangements. Analysis will be performed on de-identified samples and data sets.

6.5 In-vitro studies on Lymphoblastoid Cell Lines

Blood will be drawn for isolation of lymphocytes and other mononuclear cells (PBMCs) from whole blood using a standard Ficoll Paque density gradient centrifugation method. Mononuclear cells will be washed twice with saline solution for the generation of Epstein-Barr virus immortalized lymphoblastoid cell lines (LCLs) following standard methodology.²⁵

Baseline and cytokine induced COX-1 and -2 expression in freshly purified PBMCs and in LCLs will be detected by RT-PCR and Western blot and peptide mass spectrometry. Cyclooxygenase function will be quantitated by measuring COX products in the absence and the presence of COX inhibitors using mass spectrometry. Molecular mechanisms underlying variable COX expression and function will be elucidated using promoter studies, gene expression studies, proteomics studies and DNA sequencing. The B-cell immortalization method and the above mentioned in-vitro methodologies are routinely performed in the Institute for Translational Medicine and Therapeutics. Gene expression studies will involve both micro array technology and RNA sequencing technology. Data analysis will be based on standard software packages in Bioconductor (www.bioconductor.org) using R (cran.r-project.org). RNA sequence analysis will be performed using in-house software.

Storage of cell lines and separation of personal information from stored biological material and data will be handled analogous to the handling of stored DNA samples in compliance with lawful privacy rules.

6.6 Transcriptomics

Gene expression profiling will be performed on whole blood and/or PBMCs. Gene expression studies will involve both micro array technology and RNA sequencing technology. Data analysis will be based on standard software packages in Bioconductor (www.bioconductor.org) using R (cran.r-project.org). RNA sequence analysis will be performed using in-house software.

6.7 Proteomics

Plasma proteomics will be performed using the SomaLogic proteomics assay.²⁶

6.8 Metabolomics on Plasma and Urine Samples

Plasma and urine samples will be de-identified by transferring it into a new tube, which is labeled with a code (similar to the DNA tube labeling code) instead of the subject study number. This code will be generated using a random number generator. The study coordinator will maintain a table which contains the association between sample code and study subject information, which will not be given to the personnel who conduct and interpret the metabolomics analyses. Only non-PHI demographic information such as age, sex, race, ethnicity, BMI will be used for the analysis of the metabolomics results. Only aggregate statistics, which do not allow the identification of individual subjects, will be published. The metabolomics analysis will involve NMR spectroscopy and liquid chromatography mass spectrometry measurements. These analyses will be conducted by our collaborator, [name] at Cambridge University, UK. These measurements are entirely exploratory. Aspects such as intraindividual and interindividual variability will be assessed and can inform the design of future prospective studies into the metabolomics effects of NSAIDs.

6.9 Ambulatory Blood Pressure Monitoring (ABPM)

Ambulatory blood pressure monitors (ABPM) manufactured by Spacelab Healthcare are readily available to the investigators to assess ABP in this study protocol. The 90207 ABP monitors are compact and

lightweight to optimize subject comfort and a choice of 5 cuff sizes further aids comfort while also maximizing accuracy (retrieved from the website of the manufacturer at http://www.spacelabshealthcare.com/en/, accessed August 28, 2012).

The manufacturer indicates that the 92506 ABP Report Management System software, also readily available to the investigators, supports compliance with FDA and HIPAA requirements for integrity, availability, security, and confidentiality of protected health information (retrieved from the website of the manufacturer at http://www.spacelabshealthcare.com/en/, accessed August 28, 2012).

ABPM will be guided by the AHA Scientific Statement, Council on High Blood Pressure²⁷. Recommendations relevant to the present study are:

- Select ABP cuff size according to Table 1,
- Select the non-dominant upper arm for ABPM measurements,
- Instruct the patient to hold the arm still by their side while the device is taking a reading.

Table 1 Cuff Sizes for ARPM

Cuff Size*	Arm circumference [cm]	Arm circumference [inches]
Small Adult	17-26	7-10
Adult	24-32	9-13
Large Adult	32-42	13-17
Extra Large Adult	38-50	15-20

^{*} The bladder of the cuff should encircle at least 80% of the arm circumference. 27

The monitors for the 48-hr ambulatory blood pressure measurements will be preset to assess BP every 15 minutes in the daytime (0600h to 2200h) and every 30 minutes during the nighttime (2200h-0600h). As ABPM will be assessed over an extended period of time, 48 hours, the daytime intervals may be set to assess BP every 20 minutes to decrease the burden on the subjects and increase compliance. Preset ranges for acceptable BP measurements are 60-250 mmHg systolic, 30-200 mmHg diastolic, and 40-230 mmHg for mean arterial values. ABP readings should cover $\geq 80\%$ of the expected readings with interruptions of less than 1 hour. Awake and asleep times will be determined by patient diaries. This protocol is well established. 28,29

6.10 Stool Samples for Microbiome Analyses

Stool samples will be collected by subjects either at home or in a private bathroom within the CTRC. Subjects will be supplied with a collection kit and verbal and written instructions for stool collection at the time of consent. Stool samples will be kept frozen in a -80°C freezer until analysis. Stool form will be assessed by means of the Bristol Stool Chart, a 7-point scale.³⁰

6.11 Microbiome Analyses

DNA from stool samples, mouth and fecal swabs stored at -80°C will be extracted from each sample; PCR amplified using 16S primers, and subjected to 454/Roche pyrosequencing. At least 1000 sequence reads will be used to characterize each community. The 16S sequence reads are then aligned using the NAST and GreenGenes servers and inserted into a well characterized phylogenetic trees of 16S sequences, allowing phylogenetic placement of each sequence read. As a first step in analyzing the global effects of each treament, we will compare microbial communities using UniFrac, which quantifies the similarities among microbial communities based on phylogenetic distances. To compare two communities, sequences from both communities are placed on a common phylogenetic tree generated using ARB. The fraction of the branch length on the tree unique to each community is then measured. This provides a objective measure of community similarity based on the amount of shared

evolutionary history. To compare multiple communities, distances between all pairs of communities are computed to generate a distance matrix and Principal Coordinate Analysis is used to plot communities in a scatter plot along orthogonal axes of maximal variance. Such scatter plots can be generated taking into account the abundance as well as the presence of each taxa (weighted UniFrac), or using only presence/absence information (unweighted UniFrac). The two methods thus address different questions-weighted analysis allows differences in proportional representation of community members to be assessed, while unweighted analysis discloses changes in community composition. Measures of alpha diversity such as the Chao1 and Shannon Indices will also be used to characterize communities.

6.12 Study Visits

6.12.1 Screening Visit

All subjects will be asked to come to the Clinical and Translational Research Center (CTRC) at the Hospital of the University of Pennsylvania for the screening visit. During this visit, a complete medical history, physical examination, and the following laboratory tests will be obtained:

- Hematology: white blood cell count, red blood cell count, hemoglobin, hematocrit, MCV, MCH, MCHC, RCDW, and platelet count.
- Blood Chemistries: sodium, potassium, chloride, urea nitrogen, creatinine, fasting glucose, albumin, alkaline phosphatase, fasting cholesterol, HDL cholesterol and LDL cholesterol, triglycerides, ALT, AST, LDH, total bilirubin, GGT, uric acid, and phosphate.
- Urinalysis
- Serum and urine pregnancy test for women of childbearing potential
- Urine drug test for all subjects

Subjects will be asked to discontinue all aspirin and aspirin-containing products and herbal and dietary supplements, including vitamins and anti-oxidants, two weeks prior to beginning the treatment phase. The use of other NSAIDs and acetaminophen will be discontinued for two weeks prior to the study. Also, subjects will be asked to refrain from alcohol, caffeine, and high fat foods for 24 hours prior to all study visits and to refrain from alcohol use throughout the study.

Subjects will be asked to complete a physical activity questionnaire. They will also be asked to complete a 3-day food record to record everything they eat for 3 consecutive days.

6.12.2 Visit 1 (Baseline Visit)

Subjects will arrive in a fasting state at the CTRC at approximately 7:30 AM and will be admitted as outpatients. A urine pregnancy test will be performed in women of childbearing potential. All assessments are experimental and will be carried out for research purposes.

Blood will be drawn at approximately 7:50 AM for measurement of:

- COX-1 and COX-2 activity
- NSAID plasma concentration
- COX-1 acetylation
- PBMC isolation for transformation to LCLs
- DNA isolation

Spot urine will be collected for measurement of:

- Tx-M
- PGI-M
- PGE-M
- PGD-M
- Metabolomic analysis
- Urinary electrolytes, aldosterone, creatinine clearance, and glomerular filtration rate (GFR).

The study medication will be administered at 8 AM. Subjects will be given the study medication for the treatment phase. They will be instructed to take the medication two times a day on an empty stomach at approximately 8 AM and 8 PM with a full glass of water.

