3.4 Primary Safety Endpoints

Safety endpoints include:

- Renal function as assessed by glomerular filtration rate (GFR), sodium & potassium excretion, and creatinine in 12-hour urine as well as creatinine and urea nitrogen in plasma
- 24 hr ambulatory blood pressure at steady state

4 Subject Selection and Withdrawal

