6.12.3 Visit 2 (Whole-Day Visit)

Subjects will arrive in a fasting state at the CTRC at approximately 7:30 AM on Treatment Day 7 and will be admitted as outpatients. All assessments are experimental and will be carried out for research purposes.

Blood pressure will be measured for 24 hours using an ambulatory blood pressure monitor. Activity will be measured using an actigraph digital activity recorder. A stool sample will be collected for assessment of the gut microbiome, and subjects will complete a questionnaire regarding food consumption over the previous 24 hours.

Blood will be drawn at approximately 7:50 AM for measurement of:

- COX-1 and COX-2 activity
- Transcriptomic analysis
- Proteomic analysis
- Metabolomic analysis
- NSAID plasma concentration
- Renin activity, creatinine, and urea nitrogen
- Concentrations/ratios of major n-3/n-6 PUFAs in red blood cell membranes

Spot urine will be collected for measurement of:

- Tx-M
- PGI-M
- PGE-M
- PGD-M
- Metabolomic analysis
- Urinary electrolytes, aldosterone, creatinine clearance, and glomerular filtration rate (GFR).

The study medication will be administered at 8 AM.

Blood will be drawn 0.5, 1, 2, 4, 8, and 12 hours after administration of the study medication for measurement of:

- COX-1 and COX-2 activity
- NSAID plasma concentration

Spot urine will be collected 1, 2, 4, 8, and 12 hours after administration of the study medication for measurement of:

- Tx-M
- PGI-M
- PGE-M
- PGD-M

At 4 hours after administration of the study medication (the presumed peak of drug concentrations), blood will also be drawn for measurement of:

- Transcriptomic analysis
- Proteomic analysis
- Metabolomic analysis

Urine will be collected over 12 hours for measurement of:

Urinary electrolytes, aldosterone, creatinine clearance, and GFR.

Subjects will be discharged after the 12 hour time point (approximately 8 PM).

CONFIDENTIAL

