Attachment 8: Study Advertisement Flyer
Attachment 9: Text of Electronic Advertisement

16.1 Study Procedures Flowchart

Event	Screening Visit		reatme Phase			-Treat				eatme hase			t-Treat				reatme Phase			-Treat	
Study Day		1	2-6	7	8	9	10		25	26- 30	31	32	33	34		49	50- 54	55	56	57	58 ⁴
Hours in CTRC	2	1	0	13	1	1	1		1	0	13	1	1	1		1	0	13	1	1	1
Informed Consent	Х																				
Medical History	х																				
Physical Examination	Х																				Х
Screening Labs	Х																				Х
Urine Drug Test	Х																				
Urine Pregnancy Test	Х	Х							Х							Х					Х
Serum Pregnancy Test	Х																				Х
Urinalysis	Х																				Х
Questionnaires (3-day food record and physical activity questionnaire)	х							weeks							weeks						
Study Drug Treatment		Х	Х	Х				t - 2	Х	х	Х				ıt – 2	Х	Х	Х			
DNA		Х						Nashout -	Х						Washout	Х					
PBMCs		Х						Was	Х						Was	Х					
Questionnaire (24-hour food recall)				Х							Х							Х			
Stool Sample				Х							Х							Х			
Plasma Drug Levels		Х		X ¹	Х	Х	Х		Х		X ¹	Х	Х	Х		Х		X ¹	Х	Х	Х
COX-1 acetylation		Х							Х							Х					
COX-1 and COX-2 Activity		Х		X ¹	Х	Х	Х		Х		X ¹	Х	Х	х		Х		X ¹	Х	Х	Х
Urinary Prostaglandins and Other Metabolites		х		X ¹	х	х	х		х		X ¹	х	х	Х		х		X ¹	х	х	х
Transcriptomics				X ²							X ²							X ²			
Proteomics				X ²							X ²							X ²			
Metabolomics				X ²							X ²							X ²			
24 hr Blood Pressure Monitoring				X ³							X ³							X ³			

Blood for plasma drug levels and COX-1 and COX-2 activity will be drawn before and 0.5, 1, 2, 4, 8, and 12 hours after taking the morning dose of study drug. Spot urine will be collected before and 1, 2, 4, 8, and 12 hours after taking the morning dose of study drug. 12 hr urine will be collected for assessment of creatinine clearance.

² Blood for transcriptomics, proteomics, and metabolomics will be drawn before and 4 hours after taking the morning dose of study medication.

³ Subjects will wear an ambulatory blood pressure and activity monitor for 24 hrs. The monitor will be removed when they return to the CTRC for the first Post-Treatment Assessment.

⁴ The Close-Out Visit will occur concurrently with the final visit of Post-Treatment Assessment 3.

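### Creatinine clearance and GFR are listed under spot urine at Visits 1, 3, 4 and 5, but none of these 12 visits per subject has a timed urine collection and 11 have no blood creatinine

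*Combined protocol and SAP*

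**What the plan says.** Renal function is a secondary endpoint (section 3.3) and a primary safety endpoint (section 3.4). Both definitions include GFR, and section 3.4 specifies "creatinine in 12-hour urine as well as creatinine and urea nitrogen in plasma".

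For Visit 1, section 6.12.2 has a block that opens "Spot urine will be collected for measurement of" and ends with "Urinary electrolytes, aldosterone, creatinine clearance, and glomerular filtration rate (GFR"). Sections 6.12.4, 6.12.5 and 6.12.6 (Visits 3, 4 and 5) repeat that item, again under a spot sample.

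The blood lists at these visits are short:

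- **Visit 1**, under "Blood will be drawn at approximately 7:50 AM for measurement of": COX activity, NSAID concentration, COX-1 acetylation, PBMCs and DNA.
- **Visits 3 to 5**: COX activity and NSAID concentration only.

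Day 7 (section 6.12.3) differs. Its blood list includes "Renin activity, creatinine, and urea nitrogen", and a separate instruction reads "Urine will be collected over 12 hours for measurement of" the renal items. Footnote 1 of the flowchart (section 16.1), marked in the Day 7, 31 and 55 columns, says "12 hr urine will be collected for assessment of creatinine clearance".

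Creatinine and urea nitrogen also appear in the screening chemistries (6.12.1) and the close-out chemistries (6.12.7). Close-out coincides with Visit 5 of phase 3, which is Day 58. The monitoring plan (16.5) includes GFR in the inclusion panel but shows only CBC and platelets for the exit visit.

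**The concern.** A spot sample gives concentrations and ratios to creatinine. It gives neither a volume per unit time nor a plasma level, so it cannot yield a clearance or a GFR. The word spot does not look like loose drafting: on Day 7 the protocol separates spot urine from the 12-hour collection and lists plasma creatinine explicitly. Where the authors planned both inputs, they wrote them down.

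The protocol calls Visit 1 a baseline visit and schedules renal items there and on three days after treatment in every phase. If those values cannot be calculated, the trial loses renal change within a phase, recovery after stopping, and a check that renal function is back to its starting level when the next phase begins. Section 1.4 itself names renal toxicity as a risk of all NSAIDs.

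**Working it through.** The documents give no figure to reproduce here. The check is a tally of the schedule.

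**Required inputs.** Measured clearance = (urine creatinine × urine volume) / (plasma creatinine × collection time). Estimated GFR = a function of blood creatinine and subject characteristics. The first needs a timed urine collection and a blood creatinine; the second needs a blood creatinine.

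**Visits per subject where clearance and GFR are listed under spot urine, other than Day 7.** 4 visits × 3 phases = 12. Study days are from section 16.1; sample lists are from 6.12.2, 6.12.4 to 6.12.6 and 6.12.7.

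| Phase | Visit 1 | Visits 3, 4, 5 | Timed urine | Blood creatinine |
|---|---|---|---|---|
| 1 | Day 1 | Days 8, 9, 10 | 0 of 4 | 0 of 4 |
| 2 | Day 25 | Days 32, 33, 34 | 0 of 4 | 0 of 4 |
| 3 | Day 49 | Days 56, 57, 58 | 0 of 4 | 1 of 4 (Day 58, close-out) |
| Total | | | 0 of 12 | 1 of 12 |

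So measured clearance cannot be obtained at 12 of 12 visits, and estimated GFR cannot be obtained at 12 − 1 = 11 of 12. The three Day 7 visits (Days 7, 31 and 55) have both inputs.

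**What each phase has, counting every scheduled blood creatinine.**

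| Phase | Before treatment | Day 7 | After treatment |
|---|---|---|---|
| 1 | Screening | Yes | None |
| 2 | None | Yes | None |
| 3 | None | Yes | Day 58 |

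A 12-hour clearance exists before or after treatment in 0 of 3 phases. The scheduled sequence of blood creatinine is screening, Day 7, Day 31, Day 55, Day 58. The gaps from Day 7 onward are 31 − 7 = 24 days, 55 − 31 = 24 days and 58 − 55 = 3 days.

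**Two limits on the values outside Day 7.** No equation for estimating GFR is stated. The Day 58 value rests on section 6.12.7 and on the screening-labs mark for that day in section 16.1, while section 16.5 lists only CBC and platelets at exit.

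**The case against.** The strongest reply is that the renal endpoint never depended on these visits. Sections 3.3 and 3.4 define it on 12-hour urine with plasma creatinine and urea nitrogen, and section 16.5 places that assessment in the treatment phase. Section 6.12.3 and the flowchart footnote supply both inputs on Day 7. Neither endpoint is defined as a change from baseline or as recovery; the mention of change from baseline in section 7.2 concerns COX activity. Every subject also has a placebo phase in randomized order (section 3.1), so a placebo Day 7 value serves as the within-subject comparator. On this view the spot-urine item is a repeated line that needs tidying.

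Most of this stands. A reader might infer from the visit lists that the renal safety endpoint has no pre-treatment and no recovery value in any phase, that creatinine is drawn only on Day 7, or that the endpoint cannot be analysed. The documents support none of these. Screening gives creatinine, urea nitrogen and a GFR entry before phase 1, and close-out gives creatinine and urea nitrogen after phase 3. The Day 7 contrast with placebo is available. Spot urinary electrolytes and aldosterone remain measurable at every listed visit, though without a volume they are concentrations or ratios, not 12-hour excretion. Adjusting Day 7 for a same-phase baseline would be a refinement; no bias from omitting it has been shown.

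The reply does not make the listed values obtainable. The protocol asks for clearance and GFR at a baseline visit and three post-treatment visits per phase, and staff following it could not produce them from the samples it specifies.

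**Conclusion.** Wrong as written, with limited reach. At the 12 visits per subject outside Day 7, clearance is listed without a timed collection at all 12, and GFR without a blood creatinine at 11. Measured clearance is confined to Day 7 of each phase. Phases 2 and 3 have no creatinine baseline of their own, and phases 1 and 2 have no post-treatment creatinine. That removes within-phase change, recovery after phases 1 and 2, and a GFR check for carryover at Days 25 and 49. It does not remove the Day 7 drug-versus-placebo comparison.

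This assumes that the visit lists are complete, so that no creatinine is run on blood drawn for other purposes, and that section 6.12.7 prevails over the exit panel in section 16.5. If the exit visit has only CBC and platelets, the Day 58 value disappears, the 11 becomes 12, and no phase has a post-treatment creatinine.

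**What to change.** **Preferred.** Add plasma creatinine and urea nitrogen to the blood already drawn at Visits 1, 3, 4 and 5 (sections 6.12.2 and 6.12.4 to 6.12.6), except Day 58, which close-out covers. Report estimated GFR by a named equation. Remove creatinine clearance from the spot-urine lists, including the repeat on Day 7, and keep it for the Day 7 12-hour collection. Carry the change into the flowchart in section 16.1.

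**If no assay is added.** Delete clearance and GFR from the spot-urine lists, and state in sections 3.3 and 3.4 that the renal endpoint is the Day 7 comparison with placebo.

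**Either way.** Reconcile the exit-visit panel in section 16.5 with the close-out chemistries in section 6.12.7.

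**Cost.** The preferred change adds routine chemistry on 11 existing draws per subject, with no new visit or venepuncture. If all 288 planned subjects complete every phase, that is 288 × 11 = 3,168 samples. The fallback and the reconciliation are wording only.
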